6.11.1 Primary Efficacy Analysis

The primary endpoint for the study will be the proportion of subjects that die on study (up to Day 60). Responders are subjects who are alive at Day 60.

The number and percentage of deaths will be summarized by treatment group.

Mortality rates will be analyzed using a logistic regression model. The model will include treatment as a factor and gender, study site (or country or region), remdesivir use (No/Yes), dexamethasone use (No/Yes) and WHO Ordinal Scale strata used in randomization as covariates. The model will be fitted using logit link function. Odds ratios, standard errors, 95% confidence intervals and p-values for the treatment difference will be presented.

The primary analysis will be performed on the ITT analysis set and the ITT data scope regardless of patient's use of rescue medications, protocol violations or investigational product discontinuation consistent with the treatment policy strategy. Every effort will be made to collect vital status up to the end of the study period. Missing data for subjects who are lost to follow up will be imputed using multiple imputation methods.

Example SAS code for imputation is as follows:

```
proc mi data=xxx out=imputed1 seed=1234 n impute=50;
class treatment sex site discharge discont remdesivir dexamethasone whostrata
imputedresponse;
fcs logistic(imputedresponse / details likelihood=augment);
var treatment sex site discharge discont remdesivir dexamethasone whostrata
imputedresponse;
run;
```

where IMPUTEDRESPONSE is the response variable to be imputed, TREATMENT is the randomized treatment group (veru/placebo), SEX is sex of the subject (male/female), SITE is study site (if there are issues fitting imputation model then this might be replaced with country or region), DISCHARGE is whether the subject was discharged from the hospital at any time during the study

Controlled Quality Management Document	
	Sponsor: Veru Inc.
	Protocol Number: V3011902
STATISTICAL ANALYSIS PLAN. PHASE 2-3-4	

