(no/yes, populated as ‘no’ for subjects who were not discharged from the hospital prior to withdrawing from the study before Day 60), DISCONT is whether subject discontinued treatment early (no/yes), REMDESIVIR is the use of remdesivir at baseline (no/yes), DEXAMETHASONE is the use of dexamethasone at baseline (no/yes) and WHOSTRATA is the WHO Ordinal Scale strata used in randomization. If the imputation model does not converge when both DISCHARGE and DISCONT variables are included then will be checked if either of them alone can be included in the model. If model converges with DISCHARGE or DISCONT alone but the model with both DISCHARGE and DISCONT does not converge, then imputation model will include only DISCHARGE.

The imputed data sets will be analyzed separately for each imputation using the logistic regression model. If all subjects have the mortality status at Day 60 then the imputation part above will not be used and observed data will be analyzed as such. Example SAS code for logistic regression is as follows:

```
proc logistic data=imputed1 order=internal descending;
by _imputation_;
class imputedresponse treatment sex site remdesivir dexamethasone whostrata
  / param=glm;
model imputedresponse = treatment sex site remdesivir dexamethasone whostrata
  / clodds=both firth;
estimate 'Treatment A vs. Treatment B' treatment 1 -1 / cl e exp;
lsmeans treatment / cl exp diff;
ods output modelanova=imputed_modelanova1
  lsmeans=imputed_lsmeans1
  diffs=imputed_diffs1
  parameterestimates=imputed_parmest1;
run;
```

If there are enough deaths to perform analysis without FIRTH option then it might be dropped out. Note that variable _IMPUTATION_ identifies each of the imputations created by PROC MI.

Finally, results from individual imputations are pooled via Rubin’s rules using PROC MIANALYZE. Example SAS code for pooling log(odds) for each treatment group is as follows:

```
proc mianalyze data=imputed_lsmeans1;
by trt01pn;
modeleffects estimate;
stderr stderr;
ods output parameterestimates=combined_odds1;
```

run;

Example SAS code for pooling log(odds ratio) for each treatment group is as follows:

```
proc mianalyze data=imputed_diffs1;
  modeleffects estimate;
  stderr stderr;
  ods output parameterestimates=combined_diffs1;
run;
```

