6.11.3 Secondary Analyses for the Primary Endpoint

The primary endpoint, mortality rate at Day 60, will also be assessed in the subset of mITT patients and Safety Analysis Set (all treated subjects).

Additionally, similar analysis to primary analysis will be performed in subgroups for region, standard of care, WHO Ordinal Scale at baseline and vaccination status.

To obtain risk differences between treatment groups, the same analysis as described above for primary efficacy analysis will be performed except identity link function will be used. Example SAS code is as follows:

```
proc genmod data=a order=internal;
class treatment sex site remdesivir dexamethasone whostrata;
model response=treatment sex site remdesivir dexamethasone whostrata
  / type3 dist=bin link=identity;
lsmeans treatment / e diff exp cl;
run;
```

Additionally, mortality rates will be summarized using Kaplan-Meier (KM) survival curves and equality of treatment groups will be tested using log-rank test. Hazard ratios will be calculated using the Cox proportional hazards model including terms for treatment, gender, study site (or country or region), remdesivir use (No/Yes), dexamethasone use (No/Yes) and WHO Ordinal Scale strata used in randomization. Any subjects for whom survival status is not available at day 60 will be censored at the day of their last observed assessment or last captured event.

Example SAS code for log-rank test is as follows:

```
proc lifetest data=XXX outsurv=surv1
  plots=survival(atrisk=0 to 60 by 1);
time time*cens(1);
strata treatment;
run;
```

Example SAS code for proportional hazards model is as follows:

```
proc phreg data=XXX;
class treatment sex site remdesivir dexamethasone whostrata;
model time*cens(1)=treatment sex site remdesivir dexamethasone
  whostrata;
```

Controlled Quality Management Document		
	Sponsor:	Veru Inc.
	Protocol Number:	V3011902

```
hazardratio treatment;  
assess ph / resample seed=1234;  
run;
```

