6.11.5.5 Days in hospital

‘Days in hospital’ will be summarized using descriptive statistics (n, mean, standard deviation, median, minimum and maximum) by treatment group.

‘Days in hospital’ will be defined using two different algorithms similarly to ‘Days in ICU’.

‘Days in hospital’ will be analyzed using the same methodology as for ‘Days in ICU’ and the same sensitivity analysis will be performed except the subgroup analyses will not be performed.

6.11.5.6 The proportion of subjects that die on study at Day 15, Day 22, and Day 29.

The number and percentage for all-cause mortality will be summarized by treatment group and visit.

These endpoints will be analyzed using the same methodology as for the primary endpoint (separate analysis will be performed for each visit):

- Multiple imputation + logistic regression model
- Risk differences between treatment groups (using identity link function).

Controlled Quality Management Document			
	Sponsor:	Veru Inc.	
	Protocol Number:	V3011902	
STATISTICAL ANALYSIS PLAN. PHASE 2-3-4			

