11.1 Tables

Table Number	Table Title	Validation Method	Shell Number (if repeat)
14.1.1.1	Subject Enrollment Enrolled Set	IP	
14.1.1.2	Screen Failures Enrolled Set	IP	
14.1.1.3	Inclusion/Exclusion Criteria Violations Enrolled Set	IP	
14.1.1.4	Analysis Sets and Subject Disposition ITT Set	IP	
14.1.1.5	Protocol Deviations ITT Set	IP	
14.1.1.6	Reasons for Exclusion from Per-Protocol Set ITT Set	IP	
14.1.1.7	Randomization by Country and Site ITT Set	IP	
14.1.2.1	Demographics ITT Set	IP	
14.1.2.2	Demographics Safety Set	IP	

Controlled Quality Management Document			
	Sponsor:	Veru Inc.	
	Protocol Number:	V3011902	
STATISTICAL ANALYSIS PLAN. PHASE 2-3-4			

Table Number	Table Title	Validation Method	Shell Number (if repeat)
14.1.2.3	Demographics mITT Set	IP	14.1.2.1
14.1.2.4	Baseline Condition ITT Set	IP	
14.1.2.5	Baseline Condition Safety Set	IP	
14.1.2.6	Baseline Condition mITT Set	IP	14.1.2.3
14.1.3.1	Previous Medical History by System Organ Class and Preferred Term ITT Set	IP	
14.1.3.2	Ongoing Medical History by System Organ Class and Preferred Term ITT Set	IP	14.1.3.1
14.1.4.1	Prior Medications by ATC Level 2 and Preferred Term ITT Set	IP	
14.1.4.2	Concomitant Medications by ATC Level 2 and Preferred Term ITT Set	IP	14.1.4.1
14.1.4.3	Background Standard of Care by Country ITT Set	IP	
14.1.5.1	Treatment Exposure Safety Set	IP	
14.1.5.2	Treatment Compliance Safety Set	IP	
14.2.1.1	Proportion of Subjects Alive by Visit ITT Set	IP	
14.2.1.2	Logistic Regression for Proportion of Subjects Alive by Visit ITT Set	Stat IP	

Controlled Quality Management Document

Sponsor: Veru Inc.

Protocol Number: V3011902

STATISTICAL ANALYSIS PLAN. PHASE 2-3-4

Table Number	Table Title	Validation Method	Shell Number (if repeat)
14.2.1.3	Proportion of Subjects Alive by Visit Safety Set	IP	14.2.1.1
14.2.1.4	Logistic Regression for Proportion of Subjects Alive by Visit Safety Set	Stat IP	14.2.1.2
14.2.1.5	Proportion of Subjects Alive by Visit mITT Set	IP	14.2.1.1
14.2.1.6	Logistic Regression for Proportion of Subjects Alive by Visit mITT Set	Stat IP	14.2.1.2
14.2.1.7	Tipping Point Analysis for Proportion of Subjects Alive at Day 60 ITT Set	Stat IP	
14.2.1.8	Logistic Regression for Proportion of Subjects Alive by Visit - Identity Link ITT Set	Stat IP	14.2.1.2
14.2.1.9	Kaplan-Meier Estimates for Overall Mortality ITT Set	Stat IP	
14.2.1.10	Cox Proportional Hazards Model for Overall Mortality ITT Set	Stat IP	

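### The example PROC GENMOD code in SAP 6.11.3 does not carry out the risk-difference analysis its own text calls for: no imputation or pooling, no named event, and EXP under an identity link

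*SAP*

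**What the plan says.** **Primary analysis (SAP 6.11.1).** The endpoint is the proportion who die by Day 60, and the section adds: "Responders are subjects who are alive at Day 60". The model is fitted with "proc logistic data=imputed1 order=internal descending", on the variable IMPUTEDRESPONSE and with a `BY _imputation_` statement. The results are combined by Rubin's rules in PROC MIANALYZE. If every subject's Day 60 status is known, imputation is skipped and the observed data are analysed.

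**Risk difference (SAP 6.11.3; Protocol 9.4.2).** The text says to repeat the primary analysis and change only the link. The code that follows is labelled an example. It consists of "proc genmod data=a order=internal", a CLASS statement, "model response=treatment sex site remdesivir dexamethasone whostrata" with the options "type3 dist=bin link=identity", and "lsmeans treatment / e diff exp cl".

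**Reuse (SAP 6.11.5.6).** Mortality at Days 15, 22 and 29 is to follow the primary methodology. One bullet covers multiple imputation with logistic regression, and a separate bullet covers identity-link risk differences.

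**Output (SAP 11.1).** The only identity-link table is 14.2.1.8, "Logistic Regression for Proportion of Subjects Alive by Visit - Identity Link ITT Set". It repeats shell 14.2.1.2, the primary logistic table, which is also titled as the proportion alive.

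**The concern.** The prose and the only code given for the risk difference do not describe the same analysis. A programmer who follows the code would depart from the stated plan in three ways:

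- the missing-data method is left out;
- the modelled event is left to a software default and an undefined coding;
- an exponentiated difference is produced that is not a ratio of anything.

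The risk difference is the scale on which Protocol 9.1 presents its planning intervals, and 6.11.5.6 repeats the analysis at three further time points. At stake is whether the reported difference covers all randomized subjects, and whether a reader can tell from the table which event it refers to.

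**Working it through.** **1. The two code blocks side by side**

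| Feature | Primary, 6.11.1 | Risk difference, 6.11.3 |
|---|---|---|
| Input data set | `imputed1` | `a` |
| Response | IMPUTEDRESPONSE | RESPONSE (not defined in 6.11.3) |
| Imputation loop | `BY _imputation_` | none |
| Pooling | PROC MIANALYZE | none |
| Event order | `DESCENDING` | not given |
| Exponentiation | on the logit scale, giving odds and odds ratios | `EXP` on the identity scale |

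In the tipping-point code of 6.11.2, data set `a` is the input to PROC MI, so under that name it is not yet imputed.

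**2. The plan's own figure.** Inputs from Protocol 9.1: p1 = 0.05 (VERU-111), p2 = 0.25 (placebo), n1 = 140, n2 = 70. The interval is (p1 - p2) ± 1.96 × SE.

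SE = sqrt(0.05 × 0.95/140 + 0.25 × 0.75/70) = 0.0549

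-0.20 ± 1.96 × 0.0549 = -0.20 ± 0.108, that is -0.308 to -0.092. This matches the protocol. The interval is on the death scale, with a negative sign for benefit.

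**3. Event direction.** An unadjusted identity-link binomial model was fitted to the expected counts (alive: 133/140 and 52.5/70).

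- Modelling alive: 0.95 vs 0.75, difference +0.200 (95% CI 0.092 to 0.308).
- Modelling death: 0.05 vs 0.25, difference -0.200 (95% CI -0.308 to -0.092).

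The ratio of difference to SE is 0.20/0.0549 = 3.64 in absolute value both ways, so the p-value is the same.

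Which of the two the code gives depends on the coding of RESPONSE and on the software default. Assume that both procedures model the lowest ordered level unless told otherwise, and that RESPONSE and IMPUTEDRESPONSE are coded alike. Then `DESCENDING` in one block only makes them model opposite events. If 1 = alive, which is the direction the tipping-point section uses, Table 14.2.1.8 carries death results under an alive title. If 1 = death, the primary table is the mislabelled one.

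**4. EXP under the identity link.** exp(-0.20) = 0.819, with limits exp(-0.308) = 0.735 and exp(-0.092) = 0.912. With alive as the event it is exp(+0.20) = 1.221. For comparison:

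- death risk ratio 0.05/0.25 = 0.20
- survival risk ratio 0.95/0.75 = 1.267
- death odds ratio (0.05/0.95)/(0.25/0.75) = 0.158
- survival odds ratio 1/0.158 = 6.33

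Neither exponentiated value equals any of these. `EXP` also acts on the arm estimates: exp(0.05) = 1.051 and exp(0.25) = 1.284, both above 1 and so not proportions.

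**5. Imputation.** The documents give no missing-data rate. Assuming 2% to 10% missing at Day 60, 0.02 × 210 ≈ 4 to 0.10 × 210 = 21 subjects would be left out of a complete-case run. Scaling the half-width by 1/sqrt(1 - m), it moves from 0.108 with none missing to 0.109, 0.110 and 0.113 at 2%, 5% and 10%. The loss of precision is small. The departure lies in which subjects are analysed and what is assumed about the missing ones.

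A partial repair would do more harm. If the 50 stacked imputations replaced `a` but `BY` were still absent, the SE would shrink to about 0.0549/sqrt(50) = 0.0078 and the interval to about -0.215 to -0.185.

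**The case against.** The strongest reply is that the prose governs and is correct. The code is only an example, and the analysis it refers back to includes imputation and pooling. Data-set names in the SAP's examples are loose placeholders, so `a` need not mean un-imputed data. That stands as far as intent goes. It does not make the code consistent with the text, and the separate bullets in 6.11.5.6 make a complete-case reading easier.

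A reader might infer that the code gives a wrong or reversed treatment effect. The documents do not support that. RESPONSE is undefined in 6.11.3, and the default event is software behaviour that the SAP does not state. A negative death-scale difference is also what the endpoint and Protocol 9.1 lead one to expect. Only the table title would conflict with it.

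A reader might also infer that the exponentiated value would be reported in an odds-ratio column. `EXP` only adds output, the text asks for risk differences, and the shells are not in the documents, so this cannot be checked.

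Two safeguards count. Table 14.2.1.8 is to be independently programmed by a statistician, and Table 14.2.1.1 shows the proportions alive, so a swap of 5% and 25% for 95% and 75% should be noticed. Finally, Protocol 8.10 asks sites to establish vital status by telephone or public records. If Day 60 status is complete, the imputation point falls away at Day 60.

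**Conclusion.** The concern holds as an inconsistency between the SAP's example code and its governing sentence.

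- **Missing data.** Run as written with any Day 60 status missing, the code gives a complete-case result and not the imputed ITT analysis: 4 to 21 of 210 subjects left out at an assumed 2% to 10% missing, and none if status is complete.
- **Event.** If the two response variables are coded alike and the software default is the lowest level, the primary and risk-difference models address opposite events under the same alive title. At the planning rates with 1 = alive, the table would show -0.200 where its title implies +0.200. The size, interval width and p-value are the same either way.
- **EXP.** The added 0.82 has no interpretation.

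The primary test is unaffected, and the risk difference lies outside the Holm procedure in 6.11.7. This is worth correcting before the code is used, but it does not threaten the trial's main conclusion.

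**What to change.** In SAP 6.11.3, and so in 6.11.5.6:

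1. Fit the identity-link model to IMPUTEDRESPONSE with `BY _imputation_`, output the treatment differences and their standard errors, and pool them with PROC MIANALYZE. Use the observed data only if status is complete, as 6.11.1 already provides.
2. State the coding of the response and name the modelled event with `event=`. Death is preferable, because it matches the primary endpoint, 6.11.5.6 and the sign convention of Protocol 9.1. Adding `DESCENDING` alone is not enough: it leaves the coding undefined and, with 1 = alive, would put a section about deaths on the survival scale.
3. Remove `EXP` from the LSMEANS statement.
4. Align the title and shell of Table 14.2.1.8 with the named event, showing the risk difference and its confidence interval.

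The cost is a few lines of SAP code and one table title and shell. No new data are needed.

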- In patients with a WHO disease severity score of  $\geq 5$  at baseline, the proportion of patients that died on study (up to Day 60) in the placebo group was 46% compared to 10% in the VERU-111 treated group. This represents a 78% reduction in death in the

VERU-111 treated group compared to placebo. It is important to note that in the Phase 2 study, the 6 patients in the placebo group and the 1 patient in the VERU-111 treated group that died on study all had a WHO disease severity score of  $\geq 5$  at baseline. Therefore, randomization into the Phase 3 study will be stratified by WHO scale at baseline such that patients who have a WHO disease severity score of 4, 5, and 6 at baseline are approximately equally distributed between the treatment groups. This is a similar population as was used in the Phase 2 study and accounts for patients that move from WHO severity score of 4 to 5 and then from WHO severity score of 5 to 6 to 7 quickly.

The Phase 2 clinical study was hypothesis generating. A 78-82% reduction in mortality, a 55-65% reduction in death or respiratory failure, 3.2-fold higher mean days in ICU and 3.4-fold higher mean days on mechanical ventilation in the Placebo group compared to the VERU-111 treated group are all clinically relevant observations and warrant the continued development of VERU-111 in the treatment of SARS-CoV-2 in patients at high risk for ARDS.

There were no drug related serious adverse events (SAEs) observed in the Phase 2 clinical study of VERU-111 in SARS-CoV-2 infected patients. There were no drug related serious adverse reactions ( $\geq$ Grade 3).

The relative bioavailability (pharmacokinetics) of the VERU-111 powder in capsule (PIC) formulation has been assessed and compared to a to-be-marketed VERU-111 formulated capsule (FC) formulation. Additionally, the effect of high fat meal (food effect) was also assessed for both formulations. The data are presented in Table 1.

**Table 1 The Steady State Pharmacokinetics of VERU-111 Powder in Capsule (PIC) and Formulated Capsule (FC) Under Fasted and Fed Conditions**

	63 mg PIC (fasted)	63 mg PIC (fed)	31.5 mg FC (fasted)	31.5 mg FC (fed)
N	6	6	6	6
Cmax (ng/mL)	148.1 $\pm$ 64.7	97.8 $\pm$ 53.5	182.2 $\pm$ 32.6	169.9 $\pm$ 104.2
Tmax (hr)	2.17 $\pm$ 0.98	7.67 $\pm$ 2.66	1.67 $\pm$ 1.21	4.08 $\pm$ 2.69
AUC 0-24h (ng $\cdot$ hr/mL)	1006.16 $\pm$ 376.29	984.80 $\pm$ 519.62	973.58 $\pm$ 307.87	1011.27 $\pm$ 512.54

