## 9.0 STATISTICAL ANALYSIS

### 9.1 Sample Size Calculation

In the Phase 2, the VERU-111 treated group showed a 5.3% mortality rate compared to a 30% mortality rate in the Placebo group in the same patient population.

Approximately, 210 subjects are planned to be randomized at a 2:1 ratio into two treatment arms (140 subjects in the VERU-111 treated group and 70 subjects in the Placebo treated group). Randomization will be stratified by baseline WHO Ordinal Scale score of 4, 5 and 6 such that subjects with a WHO Ordinal Scale of 4, 5 and 6 at baseline will be approximately equally distributed between the treatment groups. Assuming a rate of mortality of 5% in the VERU-111 treated group and 25% in the Placebo treated group, the above sample sizes will yield 95% confidence interval of [-0.308, -0.092] for the risk difference between treatment groups. Other scenarios are shown in the table below.

$$\text{Confidence interval} = (p_1 - p_2) \pm z^* \sqrt{(p_1(1-p_1)/n_1 + p_2(1-p_2)/n_2)}$$

where:

- $p_1, p_2$ : sample 1 proportion, sample 2 proportion
- $z$ : the z-critical value based on the confidence level
- $n_1, n_2$ : sample 1 size, sample 2 size

Table of Alternative 95% Confidence intervals for the difference between Treatment Groups:  
 Mortality at Day 60

VERU-111	Placebo	Difference	LOWER 95% CI	UPPER 95% CI
0.05	0.15	-0.1	-0.191107629	-0.008892371
0.05	0.2	-0.15	-0.250420118	-0.049579882
0.05	0.25	-0.2	-0.307672652	-0.092327348
0.05	0.3	-0.25	-0.363261644	-0.136738356
0.1	0.15	-0.05	-0.147297482	0.047297482
0.1	0.2	-0.1	-0.206067903	0.006067903
0.1	0.25	-0.15	-0.262958399	-0.037041601
0.1	0.3	-0.2	-0.318297929	-0.081702071
0.15	0.15	0	-0.102449012	0.102449012
0.15	0.2	-0.05	-0.160812454	0.060812454
0.15	0.25	-0.1	-0.21742487	0.01742487
0.15	0.3	-0.15	-0.27256998	-0.02743002

With significance level  $\alpha=0.05$ , and a 2:1 ratio of enrollment into the VERU-111 and Placebo arms respectively, the sample size is adequate to achieve  $>92\%$  power assuming the treatment estimates stated above.

NOTE: The IDMC will monitor efficacy and safety and may make a recommendation to stop the study based on treatment success according to the statistical analysis plan and IDMC charter for this study.

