5 RANDOMIZATION

Controlled Quality Management Document		
	Sponsor:	Veru Inc.
	Protocol Number:	V3011902
STATISTICAL ANALYSIS PLAN. PHASE 2-3-4		

Randomization will be stratified by baseline WHO Ordinal Scale score of 4, 5 and 6 such that subjects with a WHO Ordinal Scale of 4, 5 and 6 at baseline are approximately equally distributed between the treatment groups.

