6.11 Efficacy Analyses

All statistical tests will be performed using a two-tailed 5% overall significance level, unless otherwise stated. All comparisons between treatments will be reported with 95% confidence intervals for the difference.

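### The supportive log-rank test of mortality leaves out the WHO randomization stratum, so it is conservative if mortality differs by WHO score

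*SAP*

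**What the plan says.** - **The test.** SAP 6.11.3 summarizes mortality with Kaplan-Meier curves and adds that "equality of treatment groups will be tested using log-rank test". Protocol 9.4.2 gives the same test. Neither names a stratification factor.
- **The code.** The PROC LIFETEST example in SAP 6.11.3 has "strata treatment" as its only STRATA statement. Without a GROUP= option, that statement defines the groups to be compared, so no stratification takes place.
- **The design.** SAP 5: "Randomization will be stratified by baseline WHO Ordinal Scale score of 4, 5 and 6". Protocol 5.1 agrees.
- **The neighbouring models.** In the SAP, the primary logistic regression (6.11.1) and the identity-link and Cox models (6.11.3) all include the WHO stratum used in randomization.
- **Prognostic strength.** Protocol 3.3 reports that the seven Phase 2 patients "that died on study all had a WHO disease severity score of" 5 or more at baseline. In that subgroup, mortality "in the placebo group was 46% compared to 10% in the VERU-111 treated group". The protocol gives this as its reason for stratifying.
- **Role.** The log-rank test is a secondary analysis of the primary endpoint. The Holm procedure in SAP 6.11.7 covers only days in ICU and days on mechanical ventilation.

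The SAP's section 9, on changes from the protocol analysis, does not mention the point.

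**The concern.** Stratified randomization holds the arms nearly balanced on WHO score. If WHO score predicts death, this balance removes part of the chance variation in the observed-minus-expected count of deaths. The unstratified log-rank variance does not know this and still counts that part. The statistic is then divided by too large a standard error, so the test rejects too rarely under the null and has less power under an alternative.

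At stake is the p-value that will accompany the mortality curves. It would be the only one of the mortality tests named above that ignores the design stratum, and the documents give no reason for the difference. It could look weaker than the WHO-adjusted Cox result in the same section for a reason unrelated to the drug.

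**Working it through.** **1. The plan's own figures.** Protocol 9.1 takes "Assuming a rate of mortality of 5% in the VERU-111 treated group and 25% in the Placebo treated group", with "140 subjects in the VERU-111 treated group and 70 subjects in the Placebo treated group".

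- SE = √(0.05×0.95/140 + 0.25×0.75/70) = 0.0549
- 95% CI = −0.20 ± 1.96×0.0549 = [−0.308, −0.092], as stated.
- Power of the two-proportion test at two-sided 0.05 is 97.5% (pooled variance) or 95.4% (unpooled). Both satisfy the stated bound of more than 92%.

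The plan gives no power or size for the log-rank test. At the planned effect, with exponential survival, HR = ln 0.95 / ln 0.75 = 0.178. Expected deaths are 140×0.05 + 70×0.25 = 24.5. Schoenfeld's formula gives Φ(√(24.5×1/3×2/3)×|ln 0.178| − 1.96) = 98.0%.

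**2. Is the stratum prognostic?** Protocol 3.3 gives 6/20 placebo deaths and 1/19 on VERU-111, all with a score of 5 or more, at rates of 46% and 10%. The implied subgroup sizes are 6/0.46 ≈ 13 and 1/0.10 = 10. Mortality was therefore 6/13 against 0/7 on placebo and 1/10 against 0/9 on VERU-111, for scores of 5 or more against lower scores. This points to a steep gradient, though it rests on seven deaths.

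**3. The two tests.** At each death time j, with d deaths (d₁ on VERU-111) among n at risk (n₁ on VERU-111):

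- U = Σ(d₁ − d·n₁/n)
- V = Σ d·(n₁/n)(1 − n₁/n)(n − d)/(n − 1)
- Z = U/√V

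The unstratified test pools everyone at risk. The stratified test computes U and V within each WHO stratum and adds them before forming Z.

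**4. Simulation.** From the documents: N = 210, 2:1 allocation, stratification by WHO 4/5/6, follow-up to Day 60, and two-sided 0.05 (SAP 6.11: "All statistical tests will be performed using a two-tailed 5% overall significance level"). Assumed, because the documents give no Phase 3 values: a stratum mix of 40/45/15% and the placebo mortality gradients below, each scaled to 25% overall. Further settings: permuted blocks of six within stratum, exponential death times, a common hazard ratio across strata, and no dropout. There were 10,000 null and 5,000 alternative replicates per row, with both tests run on the same data sets.

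Each cell is unstratified / stratified, in %. The power columns give VERU-111 against placebo mortality.

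| Placebo mortality, WHO 4/5/6 | Size | Power 5 v 25 | Power 10 v 25 | Power 15 v 25 |
|---|---|---|---|---|
| 25/25/25 (no gradient) | 5.0 / 5.1 | 98.5 / 98.5 | 80.4 / 80.5 | 43.9 / 43.8 |
| 8.9/29.6/54.2 (moderate) | 3.8 / 5.4 | 99.0 / 99.2 | 82.0 / 84.1 | 43.5 / 48.6 |
| 0.4/35.3/59.6 (Phase 2-like) | 2.2 / 4.8 | 99.1 / 99.3 | 83.2 / 87.0 | 44.1 / 51.9 |

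The simulation standard error is √(0.05×0.95/10,000) = 0.2 points for size and at most √(0.25/5,000) = 0.7 points for power. It should be smaller for differences within a row, because the two tests share data.

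**5. Reading the table.** With a gradient, the unstratified size is 2.2% to 3.8%. The power lost is 84.1 − 82.0 = 2.1 and 87.0 − 83.2 = 3.8 points at 10% v 25%, and 48.6 − 43.5 = 5.1 and 51.9 − 44.1 = 7.8 points at 15% v 25%. At the planned 5% v 25% it is 0.2 points in both rows. Without a gradient the tests agree within simulation error. Both 10% v 25% and 15% v 25% appear in the scenario table of Protocol 9.1.

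**The case against.** The strongest reply is that nothing turns on this test. The primary analysis is a logistic regression that includes the WHO stratum. The log-rank test lies outside the Holm procedure. The Cox model in the same section gives a WHO-adjusted hazard ratio, and SAP 6.11.3 also plans mortality analyses by baseline WHO score. An unadjusted log-rank test beside unadjusted Kaplan-Meier curves is a common and defensible pairing. The error is also in the safe direction, since a conservative test adds no false positives. At the planned effect the loss is negligible, and the size of any loss depends on a gradient and a stratum mix that the documents do not give for Phase 3.

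All of this stands, and it limits the weight of the point. It does not remove it. Both the text and the code leave the stratum out, so the omission cannot be put down to illustrative code. The protocol itself gives the reason to expect a gradient. The loss is visible at effects in the protocol's own scenario table.

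A reader might also expect the stratified log-rank and Cox p-values to agree. They need not: the Cox model adjusts further for gender, study site (or country or region), remdesivir and dexamethasone. Stratifying removes one avoidable source of disagreement, not all of them.

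**Conclusion.** The point holds as a modest, nearly free improvement to a supportive analysis. If mortality differs by WHO score, as Phase 2 suggests, the log-rank test as planned has a true size of about 2% to 4% instead of 5%. It then gives up about 2 to 8 power points when mortality is 10% or 15% against 25%, under 1 point at 5% against 25%, and nothing if there is no gradient. These figures rest on the assumed 40/45/15% mix, the assumed gradients, 25% placebo mortality overall and exponential survival without dropout.

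Three stronger readings are not supported:

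- **The trial loses power for its mortality claim.** It does not, because the primary logistic model already includes the stratum.
- **The false-positive risk rises.** The unstratified test errs the other way.
- **The loss is larger, with size below 2% and about 11 power points gone.** Such figures can be produced. Placebo mortality of 5/30/70% in equal strata, at a hazard ratio of 0.5, gave size 1.4% against 5.0% and power 61% against 72%. But that setting implies (5 + 30 + 70)/3 = 35% placebo mortality, above the planning value of 25% and above every placebo rate in the Protocol 9.1 table (15% to 30%).

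**What to change.** In SAP 6.11.3 and Protocol 9.4.2, state that the log-rank test is stratified by the WHO stratum used in randomization. In the example code for the test, use `strata whostrata / group=treatment;`. Produce the unstratified Kaplan-Meier curves by treatment in a separate PROC LIFETEST call, because the curves should remain one per arm. Use the same `whostrata` variable as the logistic and Cox models, so that any subject randomized under an incorrect score is handled alike throughout. The unstratified p-value may be kept if it is labelled as such.

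The cost is one phrase in each document, one changed line and one extra procedure call. It needs no new data, subjects or derived variables. The choice should be fixed before unblinding; if that has passed, report both tests and say when the stratified one was added.
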